6.3.2. Missing Dates for Adverse Events

If the adverse event start date is partially or completely missing, then the following rules will be used to impute the start date for the purpose of determining treatment emergence status only:

- If the whole start date is missing, then the start date of first drug instillation will be used.
- Missing month: if the AE has occurred the same year as start date of drug instillation, replace the missing month of onset by the month of start date of drug instillation.

If the AE has occurred the subsequent year after the year of start date of drug instillation, replace the missing month of onset by January.

If the AE has occurred the previous year of the year of start date of drug instillation, replace the missing month of onset by December.

- Missing day: if the AE has occurred the same month and year as start date of drug instillation replace the missing day of onset by the day of start date of drug instillation.

This document is confidential.

- if according to month and year the AE has occurred after the start date of drug instillation replace the missing day of onset by 01.
- if according to month and year the AE has occurred before the start date of drug instillation replace the missing day by the last day of the month.

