# Adverse Events:

All AEs (non-serious and serious) that occur during the course of the study will be recorded in the eCRF. Any pre-existing medical conditions or signs/symptoms present in a patient prior to the start of the study (i.e., before informed consent is signed) should be specified in the dedicated eCRF sections. Subsequent to signing an informed consent form, all untoward medical occurrences that occur during the course of the study must be documented on eCRF. AEs will be collected till last Follow Up visit (week 16).

When possible, signs and symptoms indicating a common underlying pathology should be documented as one comprehensive event. For each recorded event, the AE documentation must include the onset date, outcome, resolution date (if event is resolved), intensity (i.e., severity), any action with study treatment taken as a result of the event, and an assessment of the adverseevent relationship to the study treatment.

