9.3. Adverse Events / Adverse Drug Reactions

Adverse events (AEs) will be coded by SOC and PT, using the Medical Dictionary for Regulatory Activities (MedDRA 21.1).

Treatment-emergent adverse events (TEAEs) are all events occurring or worsening after the first dose of the IMP.

TEAEs will be summarized by SOC ,PT, treatment arm and phase (Treatment phase or Follow up). Both the number and percentage of patients who experience the event and the number of events will be summarised per treatment arm. Percentages will be based on the number of patients in the Safety Set.

All tables for TEAEs will be also summarized separately for each strata.

An overall summary of the number and percentage of patients and number of the events with any TEAEs, Potentially Related TEAEs, Serious TEAEs, Serious Potentially Related TEAEs, TEAEs leading to study discontinuation, TEAEs leading to death and TEAE of special interest (AESI) will be generated, and presented by treatment arm and phase (Treatment phase or Follow up)

TEAEs will be sorted alphabetically by SOC, and then sorted alphabetically by PTs within SOC.

Separate tables will be presented by severity, and for SAEs, ocular TEAEs, related ocular TEAEs, related TEAEs, and TEAEs leading to study discontinuation.

This document is confidential.

“Possible”, “probable”, “highly probable” or missing relationships are to be considered as related to study drug for the summary tables. “None” and “unlikely” relationships are to be considered not related to study drug.

Individual AEs will be listed in patient data listings. A listing of patients died due to COVID-19 will be also provided on randomized set.

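### SAP 6.3.2 imputes incomplete adverse event start dates without checking the stop date, so an event known to have ended before the first drop can be flagged treatment-emergent

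*SAP*

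**What the plan says.** SAP 6.3.2 gives rules for incomplete adverse event start dates. Their stated purpose is narrow: to "impute the start date for the purpose of determining treatment emergence status only". Four rules matter here.

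- Whole date missing: "If the whole start date is missing, then the start date of first drug instillation will be used".
- Month missing, year equal to the year of first instillation: "replace the missing month of onset by the month of start date of drug instillation".
- Day missing, month and year equal to those of first instillation: "replace the missing day of onset by the day of start date of drug instillation".
- Day missing, month earlier than that of first instillation: "replace the missing day by the last day of the month".

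SAP 9.3 defines the flag that these dates feed: "Treatment-emergent adverse events (TEAEs) are all events occurring or worsening after the first dose of the IMP".

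On collection, the Adverse Events part of Protocol 8.3 says: "Subsequent to signing an informed consent form, all untoward medical occurrences that occur during the course of the study must be documented on eCRF". For each event it requires, among other items, the onset date and the "resolution date (if event is resolved"). Protocol 6.1 sets the wash-out between screening and baseline at 7 to 9 days, and the schedule of evaluations has adverse events recorded at both visits.

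No bullet of SAP 6.3.2 mentions the stop or resolution date. Neither SAP 9.3 nor Protocol 9.5.1 adds such a condition.

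**The concern.** Assigning a doubtful event to treatment is a sound conservative default when it is not known whether the event began before or after dosing. When the recorded stop date lies before the first drop, there is no doubt left: the event can neither have begun nor have worsened after dosing. The rule still moves its start to the day of the first drop and so contradicts the definition in SAP 9.3.

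The information needed to avoid this is collected. SAP 6.3.2 also already keeps known pre-dose events pre-dose when the start month or year shows it; it does not use the same evidence from the stop date.

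The incidence and frequency of treatment-emergent events is the trial's only safety endpoint (Protocol 7.1.4, SAP 4.4). An event of the wash-out period would be counted as emerging on study drug. SAP 9.3 also treats a missing causality assessment as related, so if that field is blank the event would enter the tables of related events too.

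**Working it through.** The plan gives no figure on this point. The check is to apply the rules of SAP 6.3.2 literally to events that end before the first drop.

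**Inputs.** The imputation rules are from SAP 6.3.2 and the definition from SAP 9.3. The pre-dose window of 7 to 9 days is from Protocol 6.1. The calendar dates are illustrative assumptions.

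**Rule as applied.** With nothing known, the start is the date of first instillation. With only the year known, the month is filled first and the day second. With month and year known, only the day is filled. An imputed start on or after the day of the first drop is read as treatment-emergent (TE).

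| First drop | True onset | Stop | Part of start date known | Imputed start | Imputed start minus stop | Flag |
|---|---|---|---|---|---|---|
| 20 Jun 2019 | 13 Jun 2019 | 16 Jun 2019 | none; year; or month and year | 20 Jun 2019 | 4 days | TE |
| 3 Jul 2019 | 26 Jun 2019 | 28 Jun 2019 | none; or year | 3 Jul 2019 | 5 days | TE |
| 3 Jul 2019 | 26 Jun 2019 | 28 Jun 2019 | month and year | 30 Jun 2019 | 2 days | not TE |
| 4 Jan 2020 | 28 Dec 2019 | 30 Dec 2019 | none | 4 Jan 2020 | 5 days | TE |
| 4 Jan 2020 | 28 Dec 2019 | 30 Dec 2019 | year; or month and year | 31 Dec 2019 | 1 day | not TE |

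The table covers 3 events × 3 patterns of missing parts = 9 cases. All 9 events ended before dosing. The rule flags 3 + 2 + 1 = 6 of them as TE. With the added condition that a stop date before the first instillation means not TE, 0 of 9 are flagged.

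**Where the rule fails and where it does not.**

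- A wholly missing date always fails.
- A year-only date fails when the year is that of first instillation, even if wash-out crosses a month boundary (second row).
- A missing day fails when month and year are those of first instillation. This can also happen when wash-out begins in the previous month: with a first drop on 5 April, a start known only as April and a stop on 3 April, the imputed start is 5 April.
- A partial date known to lie in an earlier month or year stays before the first drop and is flagged correctly.

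**Reach of the missing-day branch.** Assume first-drop dates spread evenly over a 365-day year. An onset k days before the first drop falls in the previous month when the first drop is on one of the first k days of a month, that is on 12k days. The share of first-drop dates with onset in the same month is (365 − 12k)/365:

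- k = 1: 353/365 = 97%
- k = 4: 317/365 = 87%
- k = 7: 281/365 = 77%
- k = 9: 257/365 = 70%

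For an onset in the wash-out with a missing day, the failing branch is thus the usual one. These are shares of calendar dates, not of adverse events; the documents do not allow a count of events.

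**The case against.** The strongest reply is that the effect will be close to nil. Onset date is a required item (Protocol 8.3), adverse events are collected at screening and again 7 to 9 days later, and edit checks and queries address completeness and logic (Protocol 11.2). To be misclassified, an event must start and resolve inside that short window, have a stop date that shows this, and still lack part of its start date after querying. Any error adds treatment-emergent events, which is the conservative direction for safety; the rule is the same in every arm, and efficacy is untouched. All of this stands, and it makes the point minor. It does not make the rule right. Nor are incomplete wash-out dates implausible, since the protocol first instructs patients to keep a diary at baseline.

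A second reply is that SAP 9.3 speaks of events after the first dose and does not say that onset on the day of first dose counts. If it did not count, a wholly missing date would never be treatment-emergent and the imputation would defeat its evident purpose. Counting is therefore the natural reading, but it is an inference.

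A reader might also infer more than the documents support:

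- *Listings would show events ending before they began.* They would not. The imputed date serves only the treatment-emergent flag, and SAP 13.2.5.3 prints missing date parts as dashes.
- *Irritation after stopping earlier eye treatment would be a typical case.* The documents give no such frequency. Exclusion criterion 11 already bars topical dry-eye drugs within 30 days before enrolment, and preservative-free artificial tears continue through wash-out.
- *The pre-dose window is longer than 9 days.* That would be a departure from Protocol 6.1.
- *Every incomplete start date is affected.* Those known to lie in an earlier month or year are not.

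**Conclusion.** The point holds, as a small one. For three patterns of incomplete start date (wholly missing; only the year known and equal to the dosing year; only the day missing in the dosing month and year), SAP 6.3.2 can flag as treatment-emergent an event whose recorded stop date shows that it ended before the first drop. That conflicts with SAP 9.3. The rule as written gives a wrong answer; this is more than a missing detail.

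The effect is confined to the treatment-emergent flag and to the tables and listings of treatment-emergent events built on it. The number of events cannot be derived from the documents and is probably low. The error inflates counts under the same rule in all three arms. It does not bear on the primary endpoint or the sample size.

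The conclusion rests on one assumption, that onset on the day of first dose counts as treatment-emergent.

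**What to change.** Add to SAP 6.3.2:

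1. An event whose full or partial stop date shows that it ended before the first instillation is not treatment-emergent, whatever part of the start date is missing.
2. An imputed start date is never later than the stop date.
3. Where the stop date is missing, or too incomplete to show that the event ended before the first instillation, the present default (treatment-emergent) stays.
4. Onset on the day of first dose counts as treatment-emergent when its timing relative to the dose is unknown.

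The cost is a few lines in the SAP and one condition in the production and validation programs. No new data are needed. No genuine treatment-emergent event is lost, because the exclusion applies only where the recorded stop date rules out treatment emergence. The change belongs in the SAP before database lock and unmasking.

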6.4. Visit Windows

CRF visits will be used without establishing acceptable visit windows, because the study is short.

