- 11. Use of topical cyclosporine, topical corticosteroids or any other topical drug for the treatment of dry eye in either eye within 30 days of study enrolment
- 12. Contact lenses or punctum plug use during the study (previous use not an exclusion criteria but must be discontinued at the screening visit)
- 13. History of drug addiction or alcohol abuse
- 14. Any prior ocular surgery (including refractive palpebral and cataract surgery) if within 90 days before the screening visit
- 15. Participation in a clinical trial with a new active substance including medical devices during the past 60 days

16. Participation in another clinical trial study at the same time as the present study		
Test/Reference Product,	Test produ	ct is rhNGF 20 µg/ml ; reference product is vehicle .
Dosage and Mode of	Test and r	eference will be instilled in both eyes according to
Administration	the follow	ing scheme:
	Group 1:	one drop of rhNGF 20 $\mu g/ml$ will be instilled in both eyes three times daily (every 6-8 hours, e.g. 7:00 am, 02:00 pm; 09:00 pm).
	Group 2: one drop of rhNGF 20 μg/ml will be instilled in both eyes two times daily plus one drop (40 μL) of vehicle will be instilled in both eyes once daily (every 6-8 hours, e.g. 7:00 am, 02:00 pm; 09:00 pm).	
		NB: rhNGF will be instilled in the morning and in the evening while the vehicle will be instilled in the afternoon.

Version No. 2.0 - Final 08/AUG/2019

	Group 3: vehicle eye one drop will be instilled in both eyes three times daily (every 6-8 hours, e.g. 7:00 am, 02:00 pm; 09:00 pm).
	The IMP will be provided in a monthly box containing 28 daily boxes. Each daily box contains three marked vials one for each administration (e.g. 1- Morning, 2- Afternoon and 3- Evening). Together with the IMP monthly box, the patients will be provided with a sufficient number of pipette and adaptors to be used for the administration of the IMP.
	Patients will be evaluated at screening visit (day -8), baseline (day 1+2), week 2 (day 14±2), week 4 (day 28±2) or early exit and week 8 (day 56±2), 12 (day 84±4) and 16 (day 112±7) weeks of follow-up.  Screning Visit (day -8): all procedure for inclusion will be performed.  Wash-out period (from day -8 to day-1): 7 +2 days with no further treatment except commercially available preservative free artificial tears. NB: the wash-out should not be less than

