### 3.3. OVERALL STUDY DESIGN

This is a phase II, multicenter, randomized, double masked, vehicle controlled, parallel group study designed to perform dose ranging and evaluate efficacy of rhNGF eye drops at  $20~\mu g/mL$  concentration administered two or three times daily for 4 weeks in patients with moderate to severe dry eye. Patients will be evaluated at screening visit (day -8), baseline (day 1+2), week 2 (day 14±2), week 4 (day 28±2) or early withdrawal and week 8 (day 56±2), week 12 (day 84±4), week 16 (day 112±7) of follow up.

During the screening (day -8) all procedures for inclusion will be performed. From the day of screening the patients will stop any kind of further treatment, except commercially available preservative free artificial tears for a period of 7 days and 9 days as maximum (day -8 to day -1+2) until the baseline visit (day 1). At the end of the wash out period (day -8 to day -1+2), patients meeting the entry criteria for this study will be randomized 1:1:1 and treated for 4 weeks with either rhNGF eye drops  $20 \mu g/mL$  TID, rhNGF eye drops  $20 \mu g/mL$  BID and vehicle SID or vehicle TID.

Version No. 2.0 – Final 08/AUG/2019

During the 4 weeks of masked treatment only the administration of IMP it is allowed. Nevertheless, if strictly needed, the patient can take preservative free artificial tears (provided by the Sponsor). The use (n° drops/day) of preservative free artificial tears will be clearly documented in a patient's diary and in the eCRF.

Following the completion of the double-blind treatment patients will be followed up for safety assessments for an additional 12 weeks post treatment and will be evaluated at the end of the safety follow-up period. During the safety follow-up period patients will not use further treatment except preservative free artificial tears provided by the Sponsor three times daily (morning, afternoon, evening).

The use of preservative free artificial tears will be clearly documented in a patient's diary and in the eCRF.

The total duration of the study is 17 weeks.

[figure not shown]

Figure 1:Study duration

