# Interventional phase

- > Screening visit (day -8),
- ➤ Baseline (day 1+2),
- ➤ Week 2 (day 14±2),
- ➤ Week 4 (day 28±2) or early exit

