Visit 6 Follow up week 16 Final visit or early termination visit (ETV)	Day 112 ± 7	The final visit is defined as the visit performed 84 ± 7 days after the last IMP administration (i.e., at day 112 ± 7). In case of premature study discontinuation, patients will undergo an early termination visit (ETV or end of study EOS as per eCRF).  The following procedures will be performed (the below order is mandatory):  Pregnancy test for female patients of childbirth potential  Ocular examination of both eyes:  Assessment by SANDE questionnaire  Assessment by IDEEL questionnaire  Assessment by EQ-5D-3L questionnaire  Assessment by EQ-5D-3L questionnaire  Assessment of best corrected distance visual acuity (BCDVA)  External Ocular Examination  Schirmer test I (without anesthesia)  Slit-lamp examination (SLE) to assess the Eyelid - Meibomian glands, Eyelid - Erythema, Eyelid - Edema Lashes, Conjunctiva Erythema, Lens, Iris, Anterior Chamber, Corneal Horizontal Diameter  Tear Film Break-up Time (TFBUT)  Ocular surface staining (NEI score - corneal and conjunctival fluorescein staining)  Schirmer test II (with anesthesia)  Laser scanning confocal microscopy to assess goblet cells density (only selected sites)  Corneal endothelium and stroma evaluation (only the sites having a confocal microscope will do this type of evaluation)  Concomitant ocular and systemic medication  Frequency of patient's artificial tear use during 4 weeks of FU (to be reported in eCRF)  AE monitoring  During visit 6, week 16, PI or delegate must check and collect the last patient's diary concerning the third follow up period.

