The study stopped to 261 patients instead of 300 originally planned; last subject enrolled was on March 25th, 2020. On March 9th, 2020 256 patients were randomized. Among them 185 had completed the study and 44 were early terminated subjects. So only 27 subjects are ongoing and 5 not randomized at the time of national emergency due to COVID-19.

Patients affected by COVID-19 will be identified using through Adverse form and Meddra coding (Preferred Term = 'Coronavirus infection').

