3.2. Brief Description

This is a phase II, multicenter, randomized, double-masked, vehicle-controlled, parallel group study designed to perform dose ranging and evaluate efficacy of rhNGF eye drops at 20 µg/mL concentration administered two or three times daily for 4 weeks in patients with moderate to severe dry eye.

Patients will be evaluated at screening visit (day -8), baseline (Day 1), Week 2 (14 ± 2), Week 4 (Day 28 ± 2) or early withdrawal and Week 8 (Day 56 ± 2), Week 12 (Day 84 ± 4), Week 16 (Day 112 ± 7) of follow-up.

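### Early termination records have no fixed analysis visit, so they could enter the Week 16 models and tests

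*SAP*

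**What the plan says.** Four places attach early exit to the end-of-treatment visit. The protocol synopsis has "week 4 (day 28±2) or early exit and week 8 (day 56±2", Protocol 3.3 has "week 4 (day 28±2) or early withdrawal and week 8 (day 56±2", the visit list in Protocol 6 has "Week 4 (day 28±2) or early exit", and SAP 3.2 has "Week 4 (Day 28 ± 2) or early withdrawal".

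The visit table in Protocol 6.2 places it elsewhere. Its last row is headed "Visit 6 Follow up week 16 Final visit or early termination visit (ETV", carries day 112 ± 7, and gives a single procedure list for both purposes. The same row says that the eCRF calls the early visit ETV or end of study (EOS).

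For analysis, SAP 6.4 says: "CRF visits will be used without establishing acceptable visit windows, because the study is short". Two other SAP sections deal with early visits. Section 6.3.1 lets an early discontinuation visit held during treatment fill a missing Week 4 value for Schirmer I, Schirmer II, SANDE, fluorescein staining and TFBUT. Section 6.2.6 uses the date of the last visit in each period when computing artificial tear drops per day.

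**The concern.** Taking CRF visit labels as they stand is safe only if each label fixes the time of the measurement. For patients who leave early the documents give two labels, Week 4 and Week 16, and no SAP rule checks the date. A short study does not remove the problem: a patient who leaves in the first weeks and is recorded on the Visit 6 form would carry a label about three months too late.

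Week 16 is meant to describe patients 12 weeks after the last dose. It is one of four visit levels in the mixed models for the IDEEL scales and the EQ VAS (SAP 8.2.6 and 8.2.8), which give contrasts with vehicle at each visit and overall. It is also one of the PGIC visits with Wilcoxon p-values (8.2.7), and a time point for the descriptive t-tests on Schirmer I, Schirmer II, SANDE, staining and TFBUT (8.1 to 8.2.4). Values taken during treatment or early follow-up would blur that time point. If early exits or their timing differ between arms, they could also shift the comparison.

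**Working it through.** **Step 1. Follow one record through the rules.** Suppose a patient leaves on Day 10, attends an ETV, and the eCRF stores it with Visit 6.

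- *Schirmer I, Schirmer II, SANDE, staining, TFBUT:* SAP 6.3.1 carries the value to Week 4, as intended. Nothing removes the same record from the Week 16 summary and t-test.
- *IDEEL and EQ VAS:* the schedule has no Week 2 assessment, so the ETV may be this patient's only post-baseline record. The carry-forward rule does not cover these endpoints. The change enters the model as Week 16.
- *PGIC:* first collected at Week 4, so the same applies to the Week 16 Wilcoxon test.
- *Two records:* Protocol 6.3.1 asks for the follow-up assessments after discontinuation unless consent is withdrawn. A patient could have both an ETV and a true Week 16 record, and the SAP does not say which to use.

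**Step 2. How far off the label could be.** For an ETV on Days 1 to 28 labelled Week 16 (nominal day 112), the gap runs from 112 − 28 = 84 days to 112 − 1 = 111 days.

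**Step 3. How many records.** SAP section 2 says of the 256 patients randomized by 9 March 2020: "Among them 185 had completed the study and 44 were early terminated subjects". It adds 27 ongoing and 5 not yet randomized. The counts agree: 185 + 44 + 27 = 256, and 256 + 5 = 261.

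Let *a* be the number of early leavers with an ETV stored as Visit 6. Assume that each of the 185 completers has one Week 16 record and that no early leaver has a true one. The affected share is *a* / (185 + *a*):

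| *a* (assumed) | Week 16 records | Share affected |
|---|---|---|
| 0 | 185 | 0% |
| 11 | 196 | 5.6% |
| 22 | 207 | 10.6% |
| 33 | 218 | 15.1% |
| 44 | 229 | 19.2% |

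Only the endpoints of the range have a basis in the documents: zero if ETV is a separate eCRF visit, 44 if every early leaver attended an ETV and all were stored with Visit 6. As a share of all 256 randomized, the 44 are 17.2%.

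**Step 4. What it could do to an estimate.** If a fraction *p* of an arm's Week 16 values are ETV values that differ on average by *d* from the rest, the simple arm mean moves by *p* × *d*. At the ceiling that is 0.192 × *d*, about a fifth of *d*. The contrast with vehicle moves by the difference in *p* × *d* between arms. The overall contrast averages four visit levels, so about a quarter of a Week 16 shift passes into it. The documents give no basis for *d*, nor for how it differs by arm.

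**The case against.** The best reply is that the SAP already thinks of the early visit as separate. Section 6.3.1 treats an early leaver's Week 4 value as missing and the early visit as a source for it. Section 6.2.6 likewise distinguishes the last visit in a period from Week 4 and Week 16. The Protocol 6.2 row can be read as two visits sharing a procedure list, with ETV or EOS as a separate eCRF name. The Week 4 wording could then mean leaving treatment, and the Visit 6 wording leaving the study. Moreover, the primary endpoint and the change-from-baseline secondary endpoints are at Week 4, and the by-visit t-tests are descriptive.

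Much of this stands, and it rules out several stronger readings that a reader might infer:

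- *That the primary result is at risk.* For Schirmer I, section 6.3.1 sends an early visit during treatment to Week 4 whichever form it is stored on.
- *That a Day 10 value would count as an observed Week 4 value in the complete-case check.* The wording of 6.3.1 points the other way, although 6.4 does not say so.
- *That 19% of Week 16 data are mislabelled.* That is a ceiling. The 44 left at any time, including during follow-up. Protocol 6.3.2 asks for the ETV only where possible, and loss to follow-up is a listed reason for leaving.
- *That missing the Visit 3 vial reconciliation decides Per Protocol membership.* SAP 6.2.5 and 9.2 use drops given to the eligible eye, and SAP 11 drops the vial-based measure. What remains is narrower: SAP 9.1 takes administration data from the diary, Visit 3 collects the treatment diary, and the Visit 6/ETV row names only the diary for the third follow-up period.
- *That early visits mostly reflect worsening or adverse events.* Protocol 6.3.1 lists reasons for leaving without frequencies.

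The reply does not close the gap for IDEEL, EQ VAS and PGIC. Sections 6.2.6 and 6.3.1 do not reach these endpoints, and 6.4 makes the result depend on an eCRF layout that neither document fixes.

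**Conclusion.** The point holds in a limited form. The pairing of early exit with Week 4 in four places and with Week 16 in a fifth is in the current text, and SAP 6.4 adds no date check. As written, an early termination record can enter the Week 16 level of the IDEEL and EQ VAS models, their overall contrasts, the Week 16 PGIC test and the descriptive Week 16 t-tests.

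The affected share lies between 0% and 19.2% (44 of 229) on the 9 March 2020 counts. Where it falls depends on the eCRF layout, ETV attendance and when patients left, and the number who left during treatment is not given. Neither the direction nor the size of any bias can be worked out from the documents. This is a worthwhile and inexpensive correction to secondary and descriptive analyses, not a threat to the primary conclusion.

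**What to change.** In SAP 6.4, replace the statement on visit windows, as far as ETV/EOS records are concerned, with these rules:

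1. Hold ETV/EOS as its own analysis visit, classified by actual study day.
2. If it falls in the treatment period, use it as the Week 4 carry-forward source under 6.3.1.
3. Count it as an observed Week 4, 8, 12 or 16 value only if its study day lies in that visit's protocol window and no scheduled record exists.
4. Otherwise list it and leave it out of the by-visit models and tests. It should not be moved to the nearest visit: a Day 100 exit is nearest to Week 16 but outside days 105 to 119.

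Rule 3 needs one window per visit. For Week 8 the protocol gives ± 2 days in the synopsis, section 2, 3.3 and 6, but ± 4 days in the 6.2 table and 7.1, and these must be reconciled.

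In the protocol, reconcile the synopsis, 3.3 and 6 with the 6.2 table, and align SAP 3.2. State that the treatment-period diary is collected at an ETV held during treatment, because it feeds the SAP's compliance measure.

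The cost is some wording and a derived visit variable built from visit dates. There will be slightly fewer Week 16 observations, and a patient whose only post-baseline IDEEL or EQ VAS record is an out-of-window ETV will drop out of those models. If the eCRF already stores ETV separately, the rule only needs to be written down.
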